3.1.1 Screening Phase

Advertisements will be developed to recruit healthy participants from the Emory community of staff and students, and from primary care clinics at Emory Healthcare locations. A preliminary informational and pre-screening phone call will take place before scheduling an in-person screening visit at the clinical site. In addition to general health questions, we will include review

of potential COVID-19 symptoms and any known or suspected exposures during the pre-screening phone call.

These questions are:

During the past 2 weeks, have you been in close contact with anyone known to have COVID-19 disease or who tested positive for the virus?

Do you have any of the following that started in the last 2 weeks, or have you had a COVID test within the last 14 days due to COVID-related symptoms?

- Fever greater than 100 F
- Shaking/chills
- Loss of taste/smell
- Cough
- Shortness of breath or difficulty breathing
- Sore throat
- Body/muscle aches
- Headache
- Diarrhea
- Rash

If the potential subject answers Yes to any of the questions, the individual will be encouraged to seek virus testing, and will not be invited to participate in the study.

The in-person screening evaluations will occur on days -7 to 0. Within 24 hours before the in-person screening visit, another phone call will take place and the same questions about potential COVID-19 disease and any known or suspected exposures will be asked again (exception - this additional call is not needed if the in-person screening visit is scheduled the day after the pre-screening phone call above). If the potential subject answers Yes to any of the questions, the individual will be encouraged to seek virus testing, and will not be invited to participate in the study. Upon arrival at the GCRC for the in-person screening visit, the participant's temperature will be taken and participants will be asked to provide written informed consent. If consent is provided, demographic and medical history and medical record review will be conducted and an HIV test will be performed. Testing for HBV and HCV will also be performed. Inclusion and exclusion criteria will be examined. For women of reproductive

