4.1 Inclusion Criteria

- Adult age \geq 18 years & \leq 55 years
- Body mass index (BMI) $>18.5 \text{ kg/m}^2$
- At least 8 years formal education, with appropriate reading and comprehension skills
- Able and willing to provide written informed consent
- Males must agree to using contraception during the study and for 2 weeks after the last dose of study drug.
- If a female participant is of reproductive potential, the participant (and her partner) must agree to use of one of the following combinations of birth control during the study and for 2 weeks after the last dose of study drug (or tubal ligation as a single method):
 - 1) Use of a double-barrier method of contraception: condoms (male or female) and a diaphragm or cervical cap with spermicide;
 - 2) Use of an IUD and a barrier method: condoms (male or female, with or without spermicide) or a diaphragm or cervical cap with spermicide;
 - 3) Tubal ligation.

Important Note: Due to documented effects of rifabutin on effectiveness of hormonal contraceptives (16-18), these are not included as options here with the exception of an IUD. Women who are post-menopausal, defined as age greater than 45 and no menses for at least 1 year, or who have had a hysterectomy, are considered not of reproductive potential.

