3.1.4 Allocation to Interventional Group

Imatinib dose allocation will occur in an ascending manner, with safety evaluations before proceeding to the next higher dose as described in [Section 3.1.2](#).

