4.1 Inclusion Criteria

- Adult age \geq 18 years & \leq 55 years
- Body mass index (BMI) $>18.5 \text{ kg/m}^2$
- At least 8 years formal education, with appropriate reading and comprehension skills
- Able and willing to provide written informed consent
- Males must agree to using contraception during the study and for 2 weeks after the last dose of study drug.
- If a female participant is of reproductive potential, the participant (and her partner) must agree to use of one of the following combinations of birth control during the study and for 2 weeks after the last dose of study drug (or tubal ligation as a single method):
 - 1) Use of a double-barrier method of contraception: condoms (male or female) and a diaphragm or cervical cap with spermicide;
 - 2) Use of an IUD (hormonal or non-hormonal) and a barrier method: condoms (male or female, with or without spermicide) or a diaphragm or cervical cap with spermicide;

3) Use of hormone-based contraceptives (pill, patch, implant, ring, or injectable) and a barrier method: condoms (male or female, with or without spermicide) or a diaphragm or cervical cap with spermicide;

4) Tubal ligation.

Women who are post-menopausal, defined as age greater than 45 and no menses for at least 1 year, or who have had a hysterectomy, are considered not of reproductive potential.

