6.2 Study Interventions

At the time of this protocol amendment, Emory University Hospital and the GCRC are no longer requiring clinical trials to screen participants for COVID-19 symptoms. Therefore, we have removed sections pertaining to these screening procedures. However, development of COVID-19 will result in study discontinuation as in [Section 6.4](#). If routine COVID-19 screening becomes necessary again in the future, we will comply with EUH and GCRC requirements.

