8.1 Sample Size Justification and Statistical Analysis

The primary objectives are to determine the effect of imatinib on the numbers of myelomonocytic cells in the blood, assessed as the change between baseline and day 14 of

imatinib only administration. Secondary objectives include analysis of PK measurements, bacterial killing, proteomic evaluations, and immune function evaluations. We will enroll a total of 48 evaluable participants total, 12 across 4 doses of imatinib (50, 100, 200 and 400mg). 12 participants were already enrolled at the 50 mg dose, and 4 at the 100mg dose in the previous version of the protocol.

With 12 participants per dosage arm (N=48), we will have 80% power to reject the null hypothesis of no change versus the alternative hypothesis that imatinib induces an increase in the absolute numbers of myelomonocytic cells per uL of blood that is at least 0.41 of the standard deviation (SD) of the change for the cohort overall and 90% power to detect a 0.48 SD. Our primary analysis will use a linear mixed model that pools data from all time points, thus we anticipate having more power by leveraging the within-person correlation between individuals.

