There is a chance that participants will not be enrolled on all doses. Given what is known about the safety profile of imatinib, we anticipate that at least one dose will be fully enrolled. By the same rationale above, we will have 80% (90%) power to detect an increase of at least 0.89 (1.03) of a SD of the mean number of myelomonocytic cells in a specific dosage strata (using 12 per stratum). We will also have sufficient power to detect differences in effects induced by different doses. For example, comparing dose groups with a two-sample t-test, with 12 participants per dosage stratum, we would have 80% power to detect a 2.3×10^3 cells/uL difference between two arms in the change from baseline in the myelomonocytic cell count assuming a SD similar to that seen in a recent macaque study. In a preclinical study of imatinib in *Mtb*-infected antibiotic-treated treated macaques, the mean number of myelomonocytic cells increased from 1.47 ± 0.96 in controls to 3.78 ± 1.89 in imatinib treated animals, with a mean difference of 2.31 (all values indicate thousands of cells/uL). Thus we are adequately powered to detect dose-specific differences on the order of what was seen in the macaques. Further, in a supportive analysis, we will also pool the arms in order to borrow strength across the doses to fit a dose-response curve.

Myelopoiesis will be determined by estimating the absolute number of myelomonocytic cells per uL of blood using the WBC and a manual differential, as noted above. We hypothesize that, on

average, increases in myelopoiesis will occur (and the 95% CI for the change in myelopoiesis over time will exclude 0).

The same mixed model can be used for the analyses of all primary and secondary endpoints where data from all arms and time points are put into one model for the myelopoiesis count outcome. This approach should generally be a more powerful approach than the paired t-test for the change from baseline, as it is leveraging the within person correlation at all time points.

Notation: Note that day 28 terms, not shown here, can also be included similarly for those with 28-day imatinib only dosing.

Let Y_{ij} represent the cell count for individual i at time j , where $j=\text{day } 0, 14$.

Thus, Y_{i0} = count at baseline, Y_{i14} = count at day 14 for individual i .

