Similarly, let $t_{14_{ij}}$ = day14 indicator and $dose_{k_{ij}}$ = dose k indicator for individual i , time j , where $k=2,3,4$. Let r_i be the random intercept term for person i and let error_{ij} be the mean 0 independent error term for person i at time j .

$$Y_{ij} = b_0 + b_1 t_{14_{ij}} + b_2 t_{14_{ij}} * dose_{2_{ij}} + b_3 t_{14_{ij}} * dose_{3_{ij}} + b_4 t_{14_{ij}} * dose_{4_{ij}} + r_i + \text{error}_{ij}$$

b_0 = baseline myelopoiesis

b_1 = day14 change from baseline for dose 1

b_2 = difference between dose 2 and dose1 day14 change from baseline

b_3 = difference between dose 3 and dose1 day14 change from baseline

b_4 = difference between dose 4 and dose1 day14 change from baseline

$(4b_1+b_2+b_3+b_4)/4$ is the average Day 14 change from baseline pooled across the 4 doses in, i.e. the primary endpoint

$b_2 - b_3$ is the between dose difference in the day14 change from baseline for dose 2 and 3; similar comparisons can be for each distinct pair of doses for day14 change from baseline.

AE analysis

We will estimate proportion of clinical and laboratory adverse events, along with 95% exact Clopper-Pearson CI. AE rates will be summarized separately by dose and then overall. All participants who take at least 1 dose will be included in assessments of safety.

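### The Version 5.0 mixed model forces one baseline mean on four non-randomised dose groups, so dose-specific and between-dose estimates are biased if expected baselines differ

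*Combined protocol and SAP*

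**What the plan says.** The model in section 8.1 of Version 5.0 has fixed effects b0 (baseline), b1 (day 14) and b2–b4 (day 14 by doses 2, 3 and 4), plus a random intercept per person and independent error. Dose appears only in the day-14 interactions. The text defines b1 as the day-14 change at dose 1 and b2 as the "difference between dose 2 and dose1 day14 change from baseline", with b3 and b4 defined likewise. It reads b2 − b3 and similar contrasts as pairwise dose comparisons. The primary endpoint is the pooled contrast (4b1 + b2 + b3 + b4)/4.

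On allocation, section 3.1.4 of Version 5.0 says: "Imatinib dose allocation will occur in an ascending manner, with safety evaluations before proceeding to the next higher dose". Section 8.1 adds that 12 participants "were already enrolled at the 50 mg dose, and 4 at the 100mg dose" under the previous version of the protocol.

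Entry rules differ between the two supplied versions:

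- **COVID screening.** In Version 3.0 (section 3.1.1) a person reporting recent COVID-type symptoms or exposure "will be encouraged to seek virus testing, and will not be invited to participate in the study". Version 5.0 (section 6.2) notes that the site no longer requires this and states: "Therefore, we have removed sections pertaining to these screening procedures".
- **Contraception.** In section 4.1 of Version 3.0, hormonal methods are ruled out as an accepted method: "these are not included as options here with the exception of an IUD". Section 4.1 of Version 5.0 accepts "Use of hormone-based contraceptives (pill, patch, implant, ring, or injectable) and a barrier method".

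The white-cell and neutrophil eligibility limits in section 4.2 are the same in both versions.

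**The concern.** With no dose main effects, all four groups are fitted with the same baseline mean. In a randomised comparison that is correct and efficient, because expected baselines are equal by design. Here the groups are filled one after another and straddle a protocol change, so nothing in the design makes them equal. The common eligibility limits bound individual counts but do not equate group means. No section justifies the assumption.

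The primary objective in section 2.1 concerns the effects of different doses, and the dose-specific and pairwise estimates address it. If the groups' expected baselines differ, these estimates can present part of a stable group difference as a drug effect.

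**Working it through.** **1. The plan's own power figures.** Two-sided 5% is assumed, from the plan's 95% interval criterion. For a paired change the noncentrality is d√n; for two groups it is (difference/SD)√(n/2).

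- N = 48: 0.41 SD gives noncentrality 2.84 and power 79.5%; 0.48 SD gives 3.33 and 90.3%.
- n = 12: 0.89 SD gives 3.08 and 80.1%; 1.03 SD gives 3.57 and 90.0%.
- Section 8.1's example "comparing dose groups with a two-sample t-test, with 12 participants per dosage stratum": (2.3/1.89)√6 = 2.98, power 81.3%, using the SD of 1.89 in imatinib-treated macaques.

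All are reproduced. All are t-tests on change scores, so none relies on a common baseline.

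**2. What the printed model estimates.** Take complete data, n per dose, K = 4 doses and within-person correlation rho. Generalised least squares then gives

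change(k) = raw mean change(k) + (1 − rho) × (baseline mean(k) − overall baseline mean).

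The random intercept absorbs only the fraction rho of a group baseline difference. If expected baselines differ:

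- bias in dose k's change = (1 − rho) × (expected baseline of k − overall expected baseline);
- bias in a pairwise contrast = (1 − rho) × (difference in expected baselines);
- with equal groups the dose-specific biases sum to zero, so the pooled contrast is unbiased.

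**3. Numbers.** Assumptions: 12 per dose; one group's expected baseline shifted at both visits; SD of a single count = 1; rho = 0.3, 0.5 or 0.7. A shift d in one group moves the overall baseline by d/4, so that group's bias is 0.75(1 − rho)d. For d = 0.5 this is 0.26/0.19/0.11. The pairwise bias is (1 − rho)d = 0.35/0.25/0.15.

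Standard errors:

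- dose-specific, printed model: √[(1 − rho²)/12 + (1 − rho)²/48] = 0.293/0.260/0.211;
- dose-specific, with main effects: √[2(1 − rho)/12] = 0.342/0.289/0.224;
- pairwise, printed model: √[2(1 − rho²)/12] = 0.389/0.354/0.292;
- pairwise, with main effects: √[4(1 − rho)/12] = 0.483/0.408/0.316;
- pooled, either model: √[2(1 − rho)/48].

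**4. Coverage and false positives.** REML simulation, 2,000 trials per setting, t with 44 df. Coverage is for the shifted group's change; false positives are for its contrast with another dose.

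| Shift | Model | Coverage %, rho 0.3/0.5/0.7 | False positives % |
|---|---|---|---|
| 0.5 SD | printed | 86.3 / 88.4 / 91.7 | 13.9 / 10.8 / 7.1 |
| 0.5 SD | with main effects | 94.3 / 95.2 / 94.9 | 4.6 / 4.3 / 4.9 |
| 0.25 SD | printed | 93.0 / 93.5 / 95.0 | 7.4 / 6.0 / 5.4 |
| 0 | printed | 95.2 / 94.6 / 94.7 | 4.9 / 5.3 / 5.1 |

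A milder pattern was also fitted with standard mixed-model software (200 trials, rho 0.5): baselines rising evenly by 0.5 SD in total from dose 1 to dose 4, no true change. The printed model gave b1 = −0.128 and b4 = 0.266 (theory −0.125 and 0.25). With main effects they were −0.004 and 0.017. The pooled contrast was 0.011 under both.

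**5. Bias against variance.** For a dose-specific change the printed model saves variance (1 − rho)²/16 and adds squared bias (9/16)(1 − rho)²d². These balance at d = 1/3. For a pairwise contrast (1 − rho)²/6 balances (1 − rho)²d² at d = 1/√6 = 0.41. Both hold at every rho.

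**6. Unequal groups.** Section 8.2 analyses all treated participants, so sizes may differ. The pooled bias is then (1 − rho) × (unweighted − size-weighted mean baseline). With sizes 12/12/12/20, the evenly rising 0.5 SD pattern and rho 0.5, it is 0.5 × (0.250 − 0.286) = −0.018 SD.

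**The case against.** **Evidence of unequal baselines is thin.** No baseline data are given. The site, eligibility limits and counting method are unchanged. The COVID questions sit in Version 3.0 with later addenda (the base version dates from July 2019) and Version 4.0 is not supplied, so it is unclear which of the first 16 participants faced them. Version 5.0 still excludes people under treatment for significant infection. The contraception rule did not exclude hormone users who also used an accepted method, and nothing in the documents ties contraception to myeloid counts. All this stands. It leaves the size of any bias unknown; it does not supply a reason to assume equality.

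**The shift may be transient.** Suppose one group is higher by d at day 0 only and the drug does nothing. Read as a drug effect, the printed pairwise contrast is off by rho × d and the main-effects contrast by the full d. For d = 0.5 that is 0.15/0.25/0.35 against 0.50 SD, with false positives of about 7/11/22% against 17/22/34%. The arithmetic is right, so the nominal error rates with main effects apply to stable shifts. But the target the plan names is change from baseline. For that target the main-effects model is still unbiased and the printed one is still off by (1 − rho)d. Attributing that change to drug is a limit of sequential, uncontrolled groups that neither model removes.

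**The printed model is more precise and sometimes better.** For stable shifts below 0.33 SD (dose-specific) or 0.41 SD (pairwise) it has the lower mean squared error, and at 0.25 SD the loss of coverage is slight. This stands too. The case for the change rests on interval coverage and false-positive control.

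**Conclusion.** The concern holds. The printed model gives b1–b4 their stated meanings only if the four groups have equal expected baselines, which sequential, non-randomised enrolment across protocol versions does not assure. Chance imbalance between groups drawn from one population causes no bias.

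The consequence is conditional on a real difference in expected baselines: material if one group stands about 0.5 SD apart, small at 0.25 SD, and less at higher rho. Both rho and the shifts are assumptions.

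The pooled primary contrast is exactly protected with equal, complete groups, and nearly so in the unequal case tried. This should be corrected for the dose-specific and pairwise estimates; it does not threaten the primary analysis.

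**What to change.** For dose-specific and pairwise estimates, add dose main effects:

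Yij = b0 + c2·dose2 + c3·dose3 + c4·dose4 + b1·t14 + b2·t14·dose2 + b3·t14·dose3 + b4·t14·dose4 + ri + error.

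With complete data b1–b4 then equal the raw mean changes and their differences, which are the quantities behind the plan's t-test power figures. The formula for the primary contrast stays the same. The common-baseline model can remain as a sensitivity analysis. Fix the choice in advance, because the study is open-label and section 9.5.1 provides for myelopoiesis reports during its conduct.

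Section 8.1's expectation of extra power from the mixed model could also be qualified. With complete, balanced data the pooled contrast is the mean paired change, so with similar dose effects there is little to gain there.

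The cost is three fixed effects. Relative to the printed model, standard errors rise by 16/11/6% for dose-specific changes and 24/15/8% for pairwise contrasts at rho 0.3/0.5/0.7. The pooled standard error and every stated power figure are unchanged. The fix does not remove season or protocol-version effects on the day-14 change itself; the report should say so.

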After assignment to a group, each participant will be assessed for baseline data according to [Table 1](#) prior to their first imatinib dose. They will then take their first imatinib dose. Participants will then come back at various times during the 14-day period of imatinib-only dosing (see [Section 6](#) on Study Procedures). During this time, safety assessments will be performed and blood will be collected for lab assays. Participants will be given imatinib in pre-filled pill containers at study visits indicated in the schedule of events. There will also be an intensive PK study performed on day 14. On this day, participants will have an IV placed to minimize discomfort related to phlebotomy at repeated time-points after dosing. Participants will return to complete the last PK blood draw on day 15 and will then continue taking imatinib at the same dose with addition of isoniazid 300 mg and rifabutin 300 mg orally per day for the subsequent 14 days. Study visits will include safety and efficacy assessments. In addition, we will conduct a PK study on day 28, with the final PK blood draw on day 29. Volunteers will then discontinue all study drugs and will complete one additional follow-up visit at day 42, 14 days after receiving their last dose, for safety. This will conclude data collection for Cohort 1.

Cohort 2: Enrollment in Cohort 2 will occur after the PK, PD, and safety data from Cohort 1 has been reviewed and two imatinib doses have been selected for further evaluation. The screening and intervention phase for Cohort 1 is the same as for Cohort 2 in terms of data collection. However, participants in Cohort 2 will begin taking rifabutin 300 mg per day and isoniazid 300 mg per day for 14 days followed by these drugs in combination with one of two selected doses of imatinib for an additional 14 days. Volunteers will be randomized to one of the two different imatinib dose levels. PK studies and the final study visit at day 42 will be completed as for Cohort 1. The primary and secondary objectives for Cohort 2 requires evaluable myelopoiesis and PK study data through day 28 from 12 participants in both of the imatinib dose groups (total 24 participants in Cohort 2, see [Section 8.1](#) and [Section 8.2](#)).

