6.2.5 Visit 5 (Day 15)

This is a brief visit required for collection of the 24-hour blood sample for the PK study. There is no study visit window for this visit as it must occur the day after Visit 4. This is also the first day of imatinib combined with isoniazid + rifabutin administration.

- Physical Exam, Weight, and Symptoms evaluation
- Vital Signs (HR, RR, BP, Temp)
- Assessment for Adverse Effects/Unanticipated Problem Review
- PK assessment (one blood draw) at 24 hours after the previous day's study medication doses.
- Study Medication Dispensation

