The primary outcome is the change in the numbers of myelomonocytic cells in the blood between baseline and day 14 of the study. The change in these cells will be estimated with mixed models, combining all dose groups, with interactions between dose and each time point. Secondary efficacy analyses will also use mixed models to determine the relationship between imatinib exposures and change in the numbers of myelomonocytic cells at each dose separately and in the pooled dose strata. Similar analyses will be used to assess bacillary killing, as determined by the Whole Blood Bactericidal Assay (WBA), using bacille Calmette-Guerin (BCG), at day 14.

Safety

The incidence of all adverse events and in particular grade 3 or 4 adverse events and SAEs during all follow-up time will be determined using point estimates and 95% CIs.

Pharmacokinetic analysis

Pharmacokinetic (PK) parameters, including absorption, distribution, and metabolism, will be determined using S-ADAPT software utilizing a compartmental PK analysis approach and summarized by treatment regimen.

Study design

Dose-escalation trial with PK components

Power and Sample Size Analysis

At completion of the study, 48 participants with evaluable data will provide 90% power to detect a 0.48 SD in the change in the number of myelomonocytic cells on imatinib. Within each dose stratum, we will have 90% power to detect a 1.03 SD change.

Safety Evaluations

Clinical and laboratory adverse events including ECG changes will be monitored prospectively while on study drug and at 14 days after completion of imatinib.

Study Progress and Safety Monitoring Plan

The Independent Safety Monitor, PI and study team, Data Safety Monitoring Board (DSMB), and Sponsor will be responsible for monitoring the data quality and the ongoing safety of participants. Twelve participants will be enrolled into each dosage arm in an ascending manner, starting with the 100 mg imatinib dose. A safety analysis will be performed by the team and the DSMB after complete safety data are available from 6 participants within a stratum. If safe, and after a total of 12 participants are enrolled for the first stratum, then the next higher dose will begin enrolling participants. Enrollment will proceed in this manner until the sample size has been reached. Formal safety analysis will then occur using the data from all dose groups.

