1.4 Possible Drug-Drug Interactions with TB Therapy

Standard treatment of drug-susceptible TB involves two months of isoniazid, a rifamycin such as rifampin or rifabutin, pyrazinamide and ethambutol, followed by four months of isoniazid and a

rifamycin. Isoniazid inhibits CYP3A4, which could increase the concentrations of imatinib when given together (14). Both rifampin and rifabutin are inducers of cytochrome P450 enzymes, including CYP3A4. Although rifampin is the most commonly used rifamycin in TB treatment globally, in a single-dose PK study of 14 healthy human subjects rifampin reduced the mean imatinib C_{max} , AUC_{0-24} and $AUC_{0-\infty}$ by 54% (90% CI: 48–60%), 68% (64–70%) and 74% (71–76%), respectively. Rifabutin is substantially less potent in terms of inducing CYP3A and other drug-metabolizing enzymes compared to rifampin (15). In the first 16 volunteers enrolled in a previous version of this protocol that included imatinib dosing between day 14 and day 28 together with rifabutin and isoniazid, we found 50mg to be the maximum tolerated dose when given with these drugs, and an unacceptably high rate of toxicity at imatinib 100mg when given as combination therapy. These data suggest further imatinib dosing with rifabutin and isoniazid should not be conducted at 100mg or higher. However, these data do not negate the potential of imatinib as a host-directed therapy for TB, as dosing at 100mg imatinib was safe when given alone during days 1-14. New drug regimens for drug-resistant TB involve medications other than rifabutin and isoniazid, and imatinib may have benefits when given with these agents, which include oxazolidinones, nitroimidazoles, fluoroquinolones, and bedaquiline. Drug-drug interactions with these agents could occur, and studies examining these interactions would be justified if imatinib demonstrates beneficial effects at safe doses in humans, including myelopoesis and bacillary killing using the WBA assay. Therefore, our current goal is to determine if imatinib dosed alone has beneficial effects. If so, additional studies evaluating drug-drug interactions with agents other than isoniazid and rifabutin will be pursued.

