2.1 Primary Objective

- To determine the effects of different doses of imatinib on myelopoiesis in adults when given alone
- Primary Safety Objective: To determine the safety of different doses of imatinib in adults

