8.1.3 Safety Analysis

All participants entered into the study who take at least one dose of imatinib will have detailed information collected on AEs for the overall study safety analysis. An Independent Safety Monitor (ISM) will review individual and summary reports of AEs in real time as they occur, as well as scheduled formal review of AEs and clinical laboratory results on a weekly basis during the study. SAEs will be reported to the Investigator within 24 hours of awareness of occurrence and the Investigator will then assess the events and report them to the Sponsor (DAIDS), the FDA and to the Emory IRB as described in [Section 9.4](#). All SAEs will be reported to DAIDS in an expedited fashion, within 3 days of occurrence, in accordance with DAIDS requirements.

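### Version 5.0 tabulates adverse events by imatinib dose over all follow-up without separating participants assigned rifabutin plus isoniazid from day 15, so dose and regimen are mixed

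*Combined protocol and SAP*

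**What the plan says.** The primary safety objective in section 2.1 of Version 5.0 reads "To determine the safety of different doses of imatinib in adults". The Preface limits the amended protocol to imatinib given alone.

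The AE paragraph of section 8.1 (Version 5.0) plans proportions with exact Clopper-Pearson 95% intervals, and states that "AE rates will be summarized separately by dose and then overall". Everyone with at least one dose is included. Section 8.1.3 agrees: "All participants entered into the study who take at least one dose of imatinib will have detailed information collected on AEs". The Study Summary gives the window: "grade 3 or 4 adverse events and SAEs during all follow-up time will be determined".

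The 48 participants come from two regimens. Section 8.1 notes that 12 "participants were already enrolled at the 50 mg dose, and 4 at the 100mg dose" under the previous version. In that version (Version 3.0, section 3.1.2, Cohort 1), 14 days of imatinib alone were followed by continued imatinib with the "addition of isoniazid 300 mg and rifabutin 300 mg orally per day for the subsequent 14 days". The Version 3.0 entry for Visit 5 (Day 15) says "This is also the first day of imatinib combined with isoniazid + rifabutin administration". Version 5.0 section 1.4 describes the same participants as having had "imatinib dosing between day 14 and day 28 together with rifabutin and isoniazid". The 32 new participants are assigned imatinib alone for 28 days (Study Summary and section 3.1, Version 5.0).

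**The concern.** A by-dose safety table is read across the doses. Here the lowest dose carries the co-treatment in every participant after day 14, the next dose carries it in a third, and the two highest doses carry none. Any toxicity that the combination adds raises the rates at the low doses only, so it can flatten or reverse a true dose trend.

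The protocol itself says that regimen matters. The Preface and section 1.4 report unacceptable toxicity at 100 mg with the two TB drugs, and safety at 100 mg alone over days 1-14. That contrast is why Version 5.0 exists. Section 8.1 also offers day-28 terms in the cell-count model for those on 28 days of imatinib only, but the AE paragraph makes no such distinction.

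At stake is the primary safety result. As planned, the rates at 50 mg, at 100 mg and overall, including the primary safety percentage in section 3.2.1, would not be rates on imatinib alone, and the planned table carries no regimen column or label to show it.

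**Working it through.** **Reproducing the plan's counts.** Carried over: 12 + 4 = 16. New: 8 at 100 mg (section 3.1), 12 at 200 mg and 12 at 400 mg, which is 8 + 12 + 12 = 32. Total 16 + 32 = 48, as sections 4.5 and 8.1 state.

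**Regimen by dose, as planned.**

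| Dose | Days 1-14, imatinib alone | After day 14, imatinib alone | After day 14, combination | Share assigned combination |
|---|---|---|---|---|
| 50 mg | 12 | 0 | 12 | 12/12 |
| 100 mg | 12 | 8 | 4 | 4/12 |
| 200 mg | 12 | 12 | 0 | 0/12 |
| 400 mg | 12 | 12 | 0 | 0/12 |
| Overall | 48 | 32 | 16 | 16/48 = 33.3% |

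Up to day 14 the doses are comparable. After it, no imatinib-alone data exist at 50 mg.

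**Effect on the reported rate.** Let d50 and d100 be the excess, in percentage points, of participants with a qualifying event because of the combination at each dose. Then:

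- shift at 50 mg = (12/12) × d50 = d50
- shift at 100 mg = (4/12) × d100 = d100/3
- shift overall = (12 × d50 + 4 × d100)/48 = d50/4 + d100/12
- shift at 200 and 400 mg = 0

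The documents give no event counts, so d50 and d100 are assumptions. The range used is 0 to 33 points. The 33% is the frequency that section 9.5.1 says would warrant DSMB review; it is not an observed rate.

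| d50, d100 | 50 mg | 100 mg | Overall |
|---|---|---|---|
| 0, 0 | 0 | 0 | 0 |
| 0, 33 | 0 | +11.0 | +2.8 |
| 10, 10 | +10 | +3.3 | +3.3 |
| 33, 33 | +33 | +11.0 | +11.0 |

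**Extreme case at 100 mg, outside that range.** Suppose all 4 earlier participants and none of the 8 new ones have an event. The plan reports 4/12 = 33.3% (exact 95% CI 9.9-65.1%). Separated, the results are 4/4 on the combination (39.8-100%) and 0/8 on imatinib alone (0-36.9%). The overall shift is 100/12 = 8.3 points.

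**Does anything else in the plan separate the regimens?** Three places come close.

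- Section 3.2.1 limits the primary safety percentage to related events. This does not touch the table of all AEs.
- Section 8.1.1.3 keeps an optional analysis of drug concentrations against AEs in the earlier participants. It does not give rates by regimen.
- The Version 3.0 Study Summary planned a separate figure for imatinib-exposed time. Version 5.0 does not carry it, and in Cohort 1 it would have covered all 28 days, so it would not have isolated the combination days.

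**The case against.** The strongest reply has four parts.

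- **The mixture is disclosed.** Version 5.0 says in several places, including section 8.1 itself, that 16 participants came from the earlier regimen, and the by-dose summary does not forbid further splits. This is true, but disclosure elsewhere does not change what the stated rule computes.
- **The tables are descriptive.** No formal between-dose AE test is planned, and the all-follow-up rate includes 14 days of imatinib alone at every dose. Both are correct. Full confounding applies to the period after day 14 only. Even so, this is the planned summary for a primary objective.
- **Relatedness filters the primary percentage.** Version 3.0 section 9.3 had each of the three drugs assessed, so events attributed only to rifabutin or isoniazid could be left out. This stands as a partial filter. Events arising from an interaction would remain and are hard to assign to one drug. The table of all AEs has no filter.
- **The size is assumed.** The Preface names 50 mg as the maximum tolerated dose with the combination, so a large d50 sits poorly with the documents. The problem they report is at 100 mg, where the weight is 4/12 in the arm and 4/48 overall. This is fair: the 33-point row for 50 mg is an upper bound, not an expectation.

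The counts are also planned counts. Section 4.5 expects 52-60 enrolments, and the documents do not say how many of the 16 started the two drugs.

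**Conclusion.** The concern holds and should be fixed. Following the rule as written gives rates at 50 mg, 100 mg and overall that mix imatinib dose with co-treatment after day 14. The planned shares are 12/12, 4/12 and 16/48.

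The resulting distortion cannot be sized from the documents and may be zero. If the combination matters only at 100 mg, an excess of up to 33 points there moves the 100 mg rate by up to 11.0 points and the overall rate by up to 2.8. If it matters equally at 50 mg, the bounds are 33 points at 50 mg and 11.0 at 100 mg and overall. These figures rest on the planned counts and the assumed 0-33 range.

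Days 1-14, the day-14 cell-count endpoint and its power statements are unaffected.

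**What to change.** In sections 8.1 and 8.1.3 and the Study Summary of Version 5.0, keep the all-treated safety population and the section 3.2.1 endpoint. Report all AEs, and related grade 3/4 AEs or SAEs, by date of onset:

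1. Days 1-14, imatinib alone, all four doses (for earlier participants, up to the first rifabutin or isoniazid dose).
2. Day 15 to day 42, imatinib-alone participants, by dose (planned n = 0/8/12/12 at 50/100/200/400 mg).
3. Day 15 to day 42, participants who started rifabutin plus isoniazid, by imatinib dose (planned n = 12/4/0/0), with the recorded drug attribution, and not pooled with stratum 2.

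Also:

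- List separately any earlier participant followed past day 14 who never started the two drugs.
- Label any all-follow-up rate by dose or overall, including the primary safety percentage, as mixing regimens.
- State that 50 mg has no imatinib-alone rate after day 14.
- Use actual treated counts as denominators.

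The cost is wording and extra table columns, with no new visits or samples. Precision falls: with no events, the exact upper 95% limit at 100 mg after day 14 is 36.9% (0/8) on imatinib alone and 60.2% (0/4) on the combination, against 26.5% for 0/12.

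One check is needed. Section 9.2 requires all AEs to be recorded, but section 9.4 lists date of onset only for narrative reports, so confirm that an onset date is held for every AE. In the earlier participants, AE reviews at the day 14 and day 15 visits bracket the split.
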